APPENDIX 5 ACUTE GVHD GRADING AND STAGING

Table 9: Extent of Organ Involvement

Stage	Skin	Liver	Gut
1	Rash on < 25% of skin ^a	Bilirubin 2 - 3 mg/dL ^b	Diarrhea > 500 mL/day ^c or persistent nausea ^d
2	Rash on 25 - 50% of skin	Bilirubin 3 - 6 mg/dL	Diarrhea > 1000 mL/day
3	Rash on > 50% of skin	Bilirubin 6 - 15 mg/dL	Diarrhea > 1500 mL/day
4	Generalized erythroderma with bullous formation	Bilirubin >15 mg/dL	Severe abdominal pain with or without ileus
Grade^e			
I	Stage 1 - 2	None	None
II	Stage 3 or	Stage 1 or	Stage 1
III	--	Stage 2 - 3 or	Stages 2 - 4
IV^f	Stage 4	Stage 4	--

^a Use burn chart to determine extent of rash.

^b Range given as total bilirubin. Downgrade one stage if an additional cause of elevated bilirubin has been documented.

^c Volume of diarrhea applies to adults. For pediatric patients, the volume of diarrhea should be based on body surface area. Downgrade one stage if an additional cause of diarrhea has been documented.

^d Persistent nausea with histologic evidence of GVHD in the stomach or duodenum.

^e Criteria for grading given as minimum degree of organ involvement required to confer that grade.

^f Grade IV may also include lesser organ involvement with an extreme decrease in performance status.

Table 10: Percent Body Surfaces

Body Area	Percent	Total Percentage
Each Arm	9%	18%
Each Leg	18%	36%
Chest & Abdomen	18%	18%
Back	18%	18%
Head	9%	9%
Pubis	1%	1%

Stage of Chronic GVHD

Limited: Localized skin involvement resembling localized scleroderma with or without liver involvement; no other organ involvement.

Extensive: Generalized skin and/or multiple organ involvement.

APPENDIX 6 MANAGEMENT ALGORITHMS FOR IMMUNO-ONCOLOGY AGENTS

These general guidelines constitute guidance to the Investigator and may be supplemented by discussions with the Medical Monitor representing the Sponsor. The guidance applies to all immuno-oncology agents and regimens.

A general principle is that differential diagnoses should be diligently evaluated according to standard medical practice. Non-inflammatory etiologies should be considered and appropriately treated.

[figure not shown]
Corticosteroids are a primary therapy for immuno-oncology drug-related adverse events. The oral equivalent of the recommended IV doses may be considered for ambulatory patients with low-grade toxicity. The lower bioavailability of oral corticosteroids should be taken into account when switching to the equivalent dose of oral corticosteroids.

Consultation with a medical or surgical specialist, especially prior to an invasive diagnostic or therapeutic procedure, is recommended.

The frequency and severity of the related adverse events covered by these algorithms will depend on the immuno-oncology agent or regimen being used.

GI Adverse Event Management Algorithm

Rule out non-inflammatory causes. If non-inflammatory cause is identified, treat accordingly and continue I-O therapy. Opiates/narcotics may mask symptoms of perforation. Infliximab should not be used in cases of perforation or sepsis.

[figure not shown]

Patients on IV steroids may be switched to an equivalent dose of oral corticosteroids (e.g. prednisone) at start of tapering or earlier, once sustained clinical improvement is observed. Lower bioavailability of oral corticosteroids should be taken into account when switching to the equivalent dose of oral corticosteroids.

Updated 05-Jul-2016

Renal Adverse Event Management Algorithm

Rule out non-inflammatory causes. If non-inflammatory cause, treat accordingly and continue I-O therapy

[figure not shown]

Patients on IV steroids may be switched to an equivalent dose of oral corticosteroids (e.g. prednisone) at start of tapering or earlier, once sustained clinical improvement is observed. Lower bioavailability of oral corticosteroids should be taken into account when switching to the equivalent dose of oral corticosteroids.

Updated 05-Jul-2016

Pulmonary Adverse Event Management Algorithm

Rule out non-inflammatory causes. If non-inflammatory cause, treat accordingly and continue I-O therapy. Evaluate with imaging and pulmonary consultation.

[figure not shown]

Patients on IV steroids may be switched to an equivalent dose of oral corticosteroids (e.g. prednisone) at start of tapering or earlier, once sustained clinical improvement is observed. Lower bioavailability of oral corticosteroids should be taken into account when switching to the equivalent dose of oral corticosteroids.

Updated 05-Jul-2016

Hepatic Adverse Event Management Algorithm

Rule out non-inflammatory causes. If non-inflammatory cause, treat accordingly and continue I-O therapy. Consider imaging for obstruction.

Patients on IV steroids may be switched to an equivalent dose of oral corticosteroids (e.g. prednisone) at start of tapering or earlier, once sustained clinical improvement is observed. Lower bioavailability of oral corticosteroids should be taken into account when switching to the equivalent dose of oral corticosteroids.

[figure not shown]
*I-O therapy may be delayed rather than discontinued if AST/ALT ≤ 8 x ULN or T.bili ≤ 5 x ULN.

**The recommended starting dose for grade 4 hepatitis is 2 mg/kg/day methylprednisolone IV.

Updated 05-Jul-2016

Endocrinopathy Management Algorithm

Rule out non-inflammatory causes. If non-inflammatory cause, treat accordingly and continue I-O therapy. Consider visual field testing, endocrinology consultation, and imaging.

[figure not shown]

Patients on IV steroids may be switched to an equivalent dose of oral corticosteroids (e.g. prednisone) at start of tapering or earlier, once sustained clinical improvement is observed. Lower bioavailability of oral corticosteroids should be taken into account when switching to the equivalent dose of oral corticosteroids.

Updated 05-Jul-2016

Skin Adverse Event Management Algorithm

Rule out non-inflammatory causes. If non-inflammatory cause, treat accordingly and continue I-O therapy.

Patients on IV steroids may be switched to an equivalent dose of oral corticosteroids (e.g. prednisone) at start of tapering or earlier, once sustained clinical improvement is observed. Lower bioavailability of oral corticosteroids should be taken into account when switching to the equivalent dose of oral corticosteroids.

[figure not shown]
*Refer to NCI CTCAE v4 for term-specific grading criteria.

^If SJS/TEN is suspected, withhold I-O therapy and refer patient for specialized care for assessment and treatment. If SJS or TEN is diagnosed, permanently discontinue I-O therapy.

Updated 05-Jul-2016

Neurological Adverse Event Management Algorithm

Rule out non-inflammatory causes. If non-inflammatory cause, treat accordingly and continue I-O therapy.

Patients on IV steroids may be switched to an equivalent dose of oral corticosteroids (e.g. prednisone) at start of tapering or earlier, once sustained clinical improvement is observed. Lower bioavailability of oral corticosteroids should be taken into account when switching to the equivalent dose of oral corticosteroids.

Updated 05-Jul-2016

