3.5 Discontinuation of subjects following any treatment with study drug

Subjects MUST discontinue investigational product (and non-investigational product at the discretion of the investigator) for any of the following reasons:

- Subject's request to stop study treatment
- Any clinical adverse event (AE), laboratory abnormality or intercurrent illness which, in the opinion of the investigator, indicates that continued participation in the study is not in the best interest of the subject
- Termination of the study by Bristol-Myers Squibb (BMS)
- Loss of ability to freely provide consent through imprisonment or involuntarily incarceration for treatment of either a psychiatric or physical (eg, infectious disease) illness
- Additional protocol specific reasons for discontinuation [Section 4.5.5](#) and [Section 4.5.3](#)

In the case of pregnancy, the investigator must immediately notify the BMS Medical Monitor/designee of this event. In most cases, the study drug will be permanently discontinued in an appropriate manner. If the investigator determines a possible favorable benefit/risk ratio that warrants continuation of study drug and it is allowed by local regulations, a discussion between the investigator and the BMS Medical Monitor/designee must occur.

All subjects who discontinue study drug should comply with protocol specified follow-up procedures as outlined in [Table 5.1-3](#). The only exception to this requirement is when a subject

withdraws consent for all study procedures including post-treatment study follow-up or loses the ability to consent freely (ie, is imprisoned or involuntarily incarcerated for the treatment of either a psychiatric or physical illness).

If study drug is discontinued prior to the subject's completion of the study, the reason for the discontinuation must be documented in the subject's medical records and entered on the appropriate case report form (CRF) page.

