4.5.4.2 Criteria to Resume Nivolumab Dosing

Subjects may resume treatment with nivolumab when the drug-related AE(s) resolve to Grade ≤ 1 or baseline value, with the following exceptions:

- Subjects may resume treatment in the presence of Grade 2 fatigue
- Subjects who have not experienced a Grade 3 drug-related skin AE may resume treatment in the presence of Grade 2 skin toxicity
- Subjects with baseline AST/ALT or total bilirubin in the Grade 1 toxicity range who require dose delays for reasons other than a 2-grade shift in AST/ALT or total bilirubin may resume treatment in the presence of Grade 2 AST/ALT OR total bilirubin
- Subjects with combined Grade 2 AST/ALT AND total bilirubin values meeting discontinuation parameters ([Section 4.5.5](#)) should have treatment permanently discontinued
- Drug-related pulmonary toxicity, diarrhea, or colitis must have resolved to baseline before treatment is resumed
- Drug-related endocrinopathies adequately controlled with only physiologic hormone replacement may resume treatment.

If nivolumab treatment is delayed for any reason, brentuximab vedotin must also be delayed until the subject has appropriately recovered and is able to resume the combination treatment on the first day of the subsequent cycle. Brentuximab vedotin should only be given alone in case a decision has been made to permanently discontinue nivolumab.

If treatment is delayed > 6 weeks, the subject must be permanently discontinued from study therapy, except as specified in [Section 4.5.5](#).

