4.5.5 Nivolumab Treatment Discontinuation

Nivolumab treatment should be permanently discontinued for the following:

- Any Grade 2 drug-related uveitis or eye pain or blurred vision that does not respond to topical therapy and does not improve to Grade 1 severity within the re-treatment period OR requires systemic treatment
- Any Grade 3 non-skin, drug-related AE lasting > 7 days, with the following exceptions for drug-related laboratory abnormalities, drug-related uveitis, pneumonitis, bronchospasm, hypersensitivity reactions, and infusion reactions:
 - Grade 3 drug-related uveitis, pneumonitis, bronchospasm, hypersensitivity reaction, or infusion reaction of any duration requires discontinuation
 - Grade 3 drug-related endocrinopathies adequately controlled with only physiologic hormone replacement do not require discontinuation
 - Grade 3 drug-related laboratory abnormalities do not require treatment discontinuation except:
 - ◆ Grade 3 drug-related thrombocytopenia > 7 days or associated with clinically significant bleeding requires discontinuation
 - ◆ Any drug-related liver function test (LFT) abnormality that meets the following criteria require discontinuation:
 - AST or ALT > 8 x ULN
 - Total bilirubin > 5 x ULN
 - Concurrent AST or ALT > 3 x ULN and total bilirubin > 2 x ULN
- Any Grade 4 drug-related AE or laboratory abnormality, except for the following events which do not require discontinuation:
 - Grade 4 neutropenia ≤ 7 days
 - Grade 4 lymphopenia or leukopenia
 - Isolated Grade 4 electrolyte imbalances/abnormalities that are not associated with clinical sequelae and are corrected with supplementation/appropriate management within 72 hours of their onset
 - Grade 4 amylase or lipase abnormalities that are not associated with symptoms or clinical manifestations, or radiographic signs of pancreatitis. It is recommended to consult with the BMS Medical Monitor for Grade 4 amylase or lipase abnormalities
 - Grade 4 drug-related endocrinopathy AEs such as adrenal insufficiency, ACTH (Adrenocorticotropic Hormone) deficiency, hyper- or hypothyroidosis, or glucose intolerance, which resolve or are adequately controlled with physiologic hormone replacement (steroids, thyroid hormones) or glucose controlling agents, respectively, may not require discontinuation after discussion with and approval from the BMS Medical Monitor

- Any dosing delay lasting > 6 weeks from the previous dose with the following exceptions:

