 - Dosing delays to allow for prolonged steroid tapers to manage drug-related adverse events are allowed. Prior to re-initiating treatment in a subject with a dosing delay lasting > 6 weeks, the BMS medical monitor must be consulted. Tumor assessments should continue as per protocol even if dosing is delayed.
 - Dosing delays > 6 weeks that occur for non-drug-related reasons may be allowed if approved by the BMS medical monitor. Prior to re-initiating treatment in a subject with a dosing delay lasting > 6 weeks, the BMS medical monitor must be consulted. Tumor assessments should continue as per protocol even if dosing is delayed.
- Any adverse event, laboratory abnormality, or intercurrent illness which, in the judgment of the Investigator, presents a substantial clinical risk to the subject with continued nivolumab dosing.
- Disease progression as determined by investigator assessment following the guidelines given in [Appendix 2](#) and [Appendix 4](#) with the exception described in [Section 4.5.9](#).
- Subject who initiated the preparative regimen for allogeneic SCT or ASCT any time after the first dose of nivolumab treatment
- Initiation of antineoplastic therapy (ie, chemotherapy, hormonal therapy, immunotherapy, radiation therapy except for palliative radiation therapy, or standard or investigational agents for treatment of cancer)

Subjects who discontinue nivolumab due to a related AE may continue treatment with brentuximab vedotin monotherapy until disease progression or unacceptable toxicity. The same applies in case subjects discontinue brentuximab vedotin due to related AE and chose to continue on nivolumab monotherapy. During Cohort A, however, if subject meets discontinuation criteria within the DLT evaluation period, both drugs must be discontinued.

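### The Appendix 6 hepatic footnote omits the concurrent AST/ALT and bilirubin criterion and uses *or* for *and*, so it permits delay where Section 4.5.5 requires permanent nivolumab discontinuation

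*Protocol*

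**What the plan says.** Protocol Section 4.5.5 lists three drug-related liver findings that end nivolumab permanently: a transaminase above 8 times ULN, total bilirubin above 5 times ULN, or "Concurrent AST or ALT > 3 x ULN and total bilirubin > 2 x ULN". Section 3.5 makes these binding. It states that "Subjects MUST discontinue investigational product" for a list of reasons, one of which is "Additional protocol specific reasons for discontinuation", with a pointer to Sections 4.5.5 and 4.5.3. Section 4.5.4.2, on resuming nivolumab, repeats the combined rule: it names "Subjects with combined Grade 2 AST/ALT AND total bilirubin values meeting discontinuation parameters" and directs that treatment stop permanently.

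Appendix 6 holds the management algorithms for immuno-oncology (I-O) agents; Section 4.5.5.1 classes nivolumab as such an agent. The footnote to the hepatic algorithm reads: "I-O therapy may be delayed rather than discontinued if AST/ALT ≤ 8 x ULN or T.bili ≤ 5 x ULN". The appendix describes itself as general guidance to the investigator and adds that "The guidance applies to all immuno-oncology agents and regimens". The flow chart that the footnote annotates is not reproduced in the public document.

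**The concern.** The footnote carries over two of the three Section 4.5.5 liver limits and drops the third, the one for transaminase and bilirubin raised together. It also joins the two limits with *or*, so that meeting either one is enough to permit delay.

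Delay and discontinuation lead to different treatment. Under Section 4.5.4.2 a delay holds both drugs, and the combination resumes once the subject recovers. After permanent discontinuation nivolumab is not given again, and only brentuximab vedotin may continue: "Brentuximab vedotin should only be given alone in case a decision has been made to permanently discontinue nivolumab". In Cohort A the consequence is larger still: "if subject meets discontinuation criteria within the DLT evaluation period, both drugs must be discontinued". A site that relied on the footnote could therefore give nivolumab again to a subject whom Section 4.5.5 removes from it.

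**Working it through.** No sample size, power or event count is involved; the check compares two sets of thresholds. Let A be AST/ALT and B be total bilirubin, both in multiples of ULN and both drug-related.

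**Inputs**
- Section 4.5.5, stop: A > 8, or B > 5, or (A > 3 and B > 2).
- Appendix 6 footnote, delay permitted, as printed: A ≤ 8 or B ≤ 5.
- The same footnote on the reading kindest to the plan: A ≤ 8 and B ≤ 5.

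**Step 1: kind reading.** If A ≤ 8 and B ≤ 5, the first two stop conditions cannot apply, so only the concurrent one is left. Stop and permitted delay then coincide exactly where 3 < A ≤ 8 and 2 < B ≤ 5.

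**Step 2: printed wording.** With *or*, permission to delay is absent only when A > 8 and B > 5 together. It therefore also extends to A > 8 with B ≤ 5 and to B > 5 with A ≤ 8, both of which Section 4.5.5 stops.

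**Step 3: check values**

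| A | B | Section 4.5.5 | Delay permitted, *and* | Delay permitted, *or* |
|---|---|---|---|---|
| 3 | 2 | no stop | yes | yes |
| 3.1 | 2.1 | stop | yes (conflict) | yes (conflict) |
| 6 | 3 | stop | yes (conflict) | yes (conflict) |
| 8 | 5 | stop | yes (conflict) | yes (conflict) |
| 8 | 2 | no stop | yes | yes |
| 3 | 5 | no stop | yes | yes |
| 10 | 1 (normal) | stop | no | yes (conflict) |
| 10 | 3 | stop | no | yes (conflict) |
| 8.1 | 5.1 | stop | no | no |

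**Step 4: what a consistent footnote would say.** Negating the Section 4.5.5 rule gives A ≤ 8 and B ≤ 5 and not (A > 3 and B > 2). Changing *or* to *and* supplies the first two parts; the exception for concurrent elevation supplies the third. Both changes are needed.

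**The case against.** The strongest reply is that the order of authority is already clear. Section 3.5 makes the Section 4.5.5 reasons mandatory and does not cite Appendix 6. Section 4.5.4.2 points back to Section 4.5.5 for combined elevations. The appendix is generic guidance, and its footnote only permits, so a site that stops nivolumab breaches neither text. This stands. A reader might infer from the mismatch that the protocol leaves open which text governs. The documents do not support that: no sentence says outright that Section 4.5.5 prevails, but these provisions read together indicate that it does.

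A reader might also infer that Section 4.5.4.2, by naming only Grade 2 combinations, leaves higher grades uncovered. It does not. That bullet limits the exception just before it, which allows some subjects to resume with Grade 2 AST/ALT or bilirubin. Liver values of Grade 3 or higher have no exception to the resumption rule, and the concurrent criterion in Section 4.5.5 is worded for any drug-related liver test abnormality.

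Third, the unseen flow chart may state the concurrent criterion or defer to the protocol. That cannot be checked, and nothing is claimed about the chart. It does not alter the footnote as printed.

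There are also backstops. Section 4.5.5.1 urges discussion with the Medical Monitor. Events that meet the potential drug-induced liver injury definition in Section 6.6 are handled as serious adverse events and reported within 24 hours under Section 6.1.1. The second is partial: Section 6.6 excludes cases with initial cholestasis, which Section 4.5.5 does not exempt.

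**Conclusion.** The footnote is wrong as written, and the severity is low. On the kind reading it conflicts with Section 4.5.5 throughout AST/ALT above 3 and up to 8 times ULN with bilirubin above 2 and up to 5 times ULN. As printed, it conflicts everywhere that Section 4.5.5 requires a stop on these values, except where AST/ALT exceeds 8 and bilirubin exceeds 5 times ULN together.

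Section 4.5.5 is the binding rule, so the exposure is confined to a site that acts on the permissive footnote, sees the values recover to the Section 4.5.4.2 resumption criteria, and then gives nivolumab again. The documents give no basis for estimating how many subjects that could be. The conclusion assumes that the elevations are drug-related and that the footnote carries its plain meaning without the chart. No sample size, power or analysis figure is affected.

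**What to change.** Preferred: reword the footnote so that delay is allowed only *if AST/ALT ≤ 8 x ULN and T.bili ≤ 5 x ULN, and not concurrent AST/ALT > 3 x ULN with T.bili > 2 x ULN (see Section 4.5.5)*. This is the exact complement of the Section 4.5.5 liver rule, so no combination of values is left in conflict.

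If the shared algorithm has to stay as it is, add one sentence to Section 4.5.5.1: *Any discontinuation required by Section 4.5.5 applies even where an Appendix 6 algorithm would permit delay.*

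Either change is one line at the next amendment and adds no procedures, data or subjects. The footnote edit has a small downside: Sections 1.4.3 and 4.5.5.1 indicate that the algorithms also appear in the nivolumab Investigator Brochure, so the two copies must be kept consistent. The Section 4.5.5.1 sentence avoids that.

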Additional oncology clinical studies, compassionate-use programs, and postmarketing use have contributed further brentuximab vedotin safety data. Notable adverse events observed with brentuximab vedotin treatment of various cancers to date include peripheral neuropathy, infusion-related reactions, and cytopenias; and, less commonly, progressive multifocal leukoencephalopathy (PML), Stevens-Johnson syndrome (SJS), toxic epidermal necrolysis (TEN), tumor lysis syndrome (TLS), acute pancreatitis, pulmonary toxicity, and hepatotoxicity. In addition, concomitant use of brentuximab vedotin and bleomycin is contraindicated due to pulmonary toxicity that occurred in some patients receiving this combination of treatments.

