4.5.3 Dose Modifications for Brentuximab Vedotin

Table 4.5.3-1 describes the recommended dose modifications for brentuximab vedotin treatment associated toxicity. Doses reduced for brentuximab vedotin-related toxicity should not be re-escalated without discussion with the sponsor. Dose escalation of brentuximab vedotin beyond 1.8 mg/kg is not permitted.

Dose reductions below 1.2mg/kg are not allowed, and toxicities should be managed with dose delays.

If brentuximab vedotin treatment is delayed for any reason, nivolumab must also be delayed until the subject has appropriately recovered and is able to resume the combination treatment on the first day of the subsequent cycle. Nivolumab should only be given alone in case a decision has been made to permanently discontinue brentuximab vedotin.

Table 4.5.3-1: Dose Modifications for Brentuximab Vedotin				
Toxicity	Grade 1	Grade 2	Grade 3	Grade 4
Peripheral Neuropathy	Continue at same dose level	Reduce dose to 1.2 mg/kg and resume treatment ^a	Withhold (delay) until toxicity resolves to ≤ Grade 2 or baseline, then resume treatment at 1.2 mg/kg or discontinue if reduction has already occurred.	Discontinue treatment

Table 4.5.3-1: Dose Modifications for Brentuximab Vedotin				
Toxicity	Grade 1	Grade 2	Grade 3	Grade 4
Non-hematologic (except peripheral neuropathy)	Continue at same dose level	Continue at same dose level	Withhold (delay) dose until toxicity is ≤ Grade 2 or has returned to baseline, then resume treatment at the same dose level ^b	Withhold dose until toxicity is ≤ Grade 2 or has returned to baseline, then reduce dose to 1.2 mg/kg and resume treatment, or discontinue at the discretion of the investigator ^{a,b, c}
Hematologic ^d	Continue at same dose level	Continue at same dose level	Withhold (delay) until toxicity resolves to ≤ Grade 2 or baseline, then resume treatment at the same dose level ^e . Growth factor support (G-CSF or GM-CSF) should be considered for subsequent cycles. If Grade 4 neutropenia recurs despite growth factor support, consider discontinuation or dose reduction to 1.2 mg/kg.	

^a Dose reductions below 1.2 mg/kg are not allowed, and toxicities should be managed with dose delays.

^b Subjects who develop Grade 3 or 4 electrolyte laboratory abnormalities may continue study treatment without dose delay.

^c Treatment should be discontinued for subjects who experience Grade 4 infusion-related reactions.

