4.5.4 Dose Modifications for Nivolumab

4.5.4.1 Nivolumab Dose Delays

Dose delay criteria apply for all drug-related AEs. Nivolumab must be delayed until treatment can resume (see [Section 4.5.4.2](#))

Nivolumab administration should be delayed for the following:

- Any Grade ≥ 2 non-skin, drug-related AE, with the following exceptions:
 - Grade 2 drug-related fatigue or laboratory abnormalities do not require a treatment delay
- Any Grade 3 skin, drug-related AE

- Any Grade 3 drug-related laboratory abnormality, with the following exceptions for lymphopenia, leukopenia, AST, ALT, total bilirubin, or asymptomatic amylase or lipase:
 - Grade 3 lymphopenia or leukopenia does not require dose delay.
 - If a subject has a baseline AST, ALT, or total bilirubin that is within normal limits, delay dosing for drug-related Grade ≥ 2 toxicity.
 - If a subject has baseline AST, ALT, or total bilirubin within the Grade 1 toxicity range, delay dosing for drug-related Grade ≥ 3 toxicity.
- Any AE, laboratory abnormality, or intercurrent illness which, in the judgment of the investigator, warrants delaying the dose of study medication.

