4.5.5.1 Management Algorithms for Immuno-Oncology Agents

Immuno-oncology (I-O) agents are associated with AEs that can differ in severity and duration than AEs caused by other therapeutic classes. Nivolumab is considered an immuno-oncology agent in this protocol. Early recognition and management of AEs associated with immuno-oncology agents may mitigate severe toxicity. Management algorithms have been developed to assist investigators in assessing and managing the following groups of AEs:

Gastrointestinal

Renal

Pulmonary

Hepatic

Endocrinopathies

Skin

Neurological

For subjects expected to require more than 4 weeks of corticosteroids or other immunosuppressants to manage an AE, consider recommendations provided in the algorithms. These algorithms are found in [Appendix 6](#) and the Nivolumab IB. Discussions with the BMS Medical Monitor on how to apply these algorithms are strongly encouraged. The guidance provided in these algorithms should not replace the Investigator's medical judgment but should complement it.

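### For diagnosed, drug-related SJS/TEN below Grade 4, Appendix 6 permanently stops nivolumab while Sections 4.5.4 and 4.5.5 delay it and allow it to resume, and nothing says which text governs

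*Protocol*

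**What the plan says.** **Appendix 6, skin algorithm footnote.** Immuno-oncology therapy is withheld when SJS or TEN is suspected, and then: "If SJS or TEN is diagnosed, permanently discontinue I-O therapy". The text of the footnote states no grade. Section 4.5.5.1 identifies the drug concerned: "Nivolumab is considered an immuno-oncology agent in this protocol".

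**Section 4.5.4.1.** The grade-based skin trigger for delaying nivolumab is "Any Grade 3 skin, drug-related AE". A separate bullet allows a delay for any event that the investigator thinks warrants one.

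**Section 4.5.4.2.** "Subjects may resume treatment with nivolumab when the drug-related AE(s) resolve to Grade ≤ 1 or baseline value". Exceptions follow, and none of them names SJS or TEN.

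**Section 4.5.5.** The Grade 3 stopping rule is "Any Grade 3 non-skin, drug-related AE lasting > 7 days". Related Grade 4 events also stop nivolumab, and no skin event is among the exceptions. A further bullet stops nivolumab when the investigator judges the risk of continuing to be substantial.

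**Standing of the texts.** Appendix 6 opens with: "These general guidelines constitute guidance to the Investigator and may be supplemented by discussions with the Medical Monitor representing the Sponsor". Section 4.5.5.1 says the algorithms complement the investigator's judgment and do not replace it. Section 3.5 makes the reasons in Sections 4.5.5 and 4.5.3 mandatory grounds for discontinuation and does not mention Appendix 6.

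**Brentuximab vedotin.** Section 1.4.4 lists SJS and TEN among the less common notable events with this drug. Table 4.5.3-1 has no entry for either. Its row for Grade 3 non-hematologic toxicity says: "Withhold (delay) dose until toxicity is ≤ Grade 2 or has returned to baseline, then resume treatment at the same dose level".

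**The concern.** A permanent stop for a severe skin reaction appears only in a footnote to a guidance appendix. The sections a site would use to decide on the next nivolumab dose lead to a delay with possible resumption. An investigator who works from Section 4.5 and one who works from Appendix 6 can both believe they are following the protocol.

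Patient safety is the first stake. The second is measurement: adverse events leading to discontinuation and adverse events leading to dose delay are both primary safety endpoints (Protocol Section 8.3.1, SAP Section 4.1), and the text a site follows affects how the event is counted. The third is Cohort A. Under Section 4.5.5, a subject who meets discontinuation criteria within the DLT period must stop both drugs, and the protocol does not say whether the Appendix 6 stop is such a criterion.

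**Working it through.** No figure in the plan needs reproducing. The check sets the passages side by side for nivolumab, given a diagnosed, drug-related SJS or TEN.

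| Grade | Appendix 6 footnote | Sections 4.5.4.1, 4.5.4.2 and 4.5.5 | Agree? |
|---|---|---|---|
| 4 | Permanent stop | Stop; no skin exception | Yes |
| 3 | Permanent stop | Delay; may resume at Grade 1 or lower, or baseline; stop if the investigator so judges | No |
| Below 3, if so graded | Permanent stop | No grade-based skin trigger; delay or stop only on investigator judgment | No |

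**Step 1: the Grade 3 row.** The Grade 3 stop in Section 4.5.5 excludes skin events by its own wording, so the event falls to the delay rule and then to the resumption rule. Delays beyond 6 weeks also end nivolumab, with exceptions such as prolonged steroid tapers. Resumption is therefore open mainly to subjects who recover within that time. The footnote has no recovery route.

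**Step 2: which text governs.** Section 3.5 gives Section 4.5.5 mandatory force. Section 4.5.5 refers to Appendices 2 and 4 when it defines progression as a stopping reason, but its toxicity bullets do not refer to Appendix 6. Section 4.5.5.1 does point to Appendix 6, but as support for judgment. No sentence ranks the two.

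**Step 3: Cohort A.** If the footnote counts as a discontinuation criterion, a Grade 3 case in the DLT period stops both drugs. If it does not, nivolumab is delayed and Table 4.5.3-1 would let brentuximab resume. The protocol does not say which applies. SAP Section 7.6.1 also includes discontinuation required by a related event among the routes to a DLT.

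**Step 4: brentuximab.** The footnote covers immuno-oncology therapy only, so Table 4.5.3-1 cannot contradict it. What remains is a missing entry. By contrast, PML, which is in the same Section 1.4.4 list, has its own rule for both drugs in Section 4.5.7.

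**Step 5: effect on the safety counts.** One reclassified subject changes a cohort's discontinuation proportion by 1/n. With the planned Cohort B sizes this is 1/40 = 2.5% (DLBCL), 1/30 = 3.3% (PTCL and PMBL), 1/20 = 5% (CTCL), 1/10 = 10% (MGZL) and 1/130 = 0.8% overall. SAP Section 7.1 pools Cohort A with Cohort B, so the actual denominators would be slightly larger.

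**The case against.** The strongest reply is that nothing in Section 4.5 obliges a site to give nivolumab again. Resumption is permissive, so a site that applies the Appendix 6 stop breaches nothing. Section 4.5.5.1 sends investigators to Appendix 6 for skin events and strongly encourages discussion with the medical monitor. Sections 3.5 and 4.5.5 both require a stop when the investigator judges that continuing is not in the subject's interest or carries substantial risk. This stands as far as it goes: the body text permits resumption and does not require it. The conflict remains all the same, because a judgment clause allows a stop that the footnote makes unconditional.

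A reader might infer several stronger points that the documents do not support:

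- **Suspected SJS/TEN.** Withholding on suspicion is compatible with Section 4.5.4.1, which allows a delay on investigator judgment. The conflict concerns diagnosed events.
- **Brentuximab re-dosed against Appendix 6.** The footnote does not reach brentuximab. The study design text (Section 3.1) also limits single-agent continuation to the drug that is not causing the toxicity.
- **All grades.** At Grade 4 the nivolumab texts agree.

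The skin algorithm figure is not shown, so the box to which the footnote attaches cannot be seen. The point rests on the footnote's words, which carry no grade limit.

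**Conclusion.** The conflict holds, within limits. It concerns nivolumab, for diagnosed and drug-related SJS or TEN below Grade 4. There Appendix 6 requires a permanent stop, Sections 4.5.4.1, 4.5.4.2 and 4.5.5 allow delay and resumption, and no text says which prevails or whether the appendix stop counts as a discontinuation criterion in Cohort A. The brentuximab matter is a separate gap and not a contradiction.

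The number of subjects affected cannot be given. The documents report no incidence for the combination and do not say how SJS or TEN would be graded, so the share below Grade 4 is unknown. A reader might be tempted to put an assumed incidence on it, but no figure in the documents would support one. Effects on the safety counts are per event, as shown in the working, and are largest in the smallest cohort. SAP Section 7.1 describes the Cohort A dose exploration in the past tense, so the Cohort A question may by then bear more on classification than on dosing.

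The case for correcting this rests on the seriousness of the event and the low cost of the change, not on expected frequency.

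**What to change.** In the next protocol amendment:

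1. Reconcile Sections 4.5.4.1, 4.5.4.2 and 4.5.5 with the Appendix 6 skin footnote, so that one nivolumab instruction for diagnosed SJS/TEN appears in all of them. Which clinical rule that should be is for the sponsor's medical team to choose.
2. State, for example in Section 4.5.5.1, which text governs when Appendix 6 and Section 4.5 differ.
3. State whether a stop under Appendix 6 counts as a discontinuation criterion for Section 3.5 and for the Cohort A two-drug stop.
4. Separately, confirm whether the generic non-hematologic row of Table 4.5.3-1 is meant to apply to SJS/TEN under brentuximab, and say so in the table.

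The cost is a few sentences and one table note. No procedures, visits or subjects are added.
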